Endpoints	
 - Time varying number and proportion of children infected with SARS-CoV-2 secondary to an infected classmate (transmission rate inside school but from a child to a child). - Time varying number and proportion of adult school-attenders infected with SARS-CoV-2 secondary to an asymptomatic infected child (transmission rate inside school but from a child to an adult); - Time varying number and proportion of children infected with SARS-CoV-2 secondary to an infected adult school attender (transmission rate inside school but from an adult to a child);

	
 - Time varying number and proportion of children infected with SARS-CoV -2 secondary to a household contact or outside the school (transmission rate from outside school).
Statistical analyses plan	
Sample size determination
 
As a pilot study, no formal sample size calculation was performed. The expected number of children is 2400, the expected number of adult school attenders is 200, and the expected number of classes is 72.
 
Initial incidence and then secondary attack rates will be calculated and compared between gender, across age, and between the three kinds of schools using Poisson or Binomial negative regression if overdispersion. Analyses will be weighted to correct for cluster effect of classes (ICC=0.09).

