3.4 Endpoints

- Time varying number and proportion of children infected with SARS-CoV-2 secondary to an asymptomatic infected classmate (transmission rate inside school with the child being the infector).

- Time varying number and proportion of adult school-attenders infected with SARS-CoV-2 secondary to an asymptomatic infected child (transmission rate inside school but from a child to an adult);
- Time varying number and proportion of children infected with SARS-CoV-2 secondary to an infected adult school-attender (transmission rate inside school but from an adult to a child);
- Time varying number and proportion of children infected with SARS-CoV-2 secondary to a household contact or outside the school (transmission rate from in the community).

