4.4.3 Definitions

4.4.3.1 Asymptomatic versus symptomatic cases

- A positive case: a participant who has a positive PCR salivary test for SARS-CoV-2 detected by systematic weekly screening
- Asymptomatic case: a participant who has a positive salivary test for SARS-CoV-2 during the study period and who did not declare any symptoms compatible with COVID-19
- Symptomatic case: a participant who has a positive salivary test with symptoms compatible with COVID-19 during the study period

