5.2 Follow-up visit

All participants, children attending selected schools and adults school attenders, will be asked to provide a weekly salivary specimen for six consecutive weeks.

All participants, children attending selected schools and adult school attenders, will have to complete a follow-up questionnaire, once a week for six consecutive weeks (See attached file) providing information about

- any compatible symptom with a SARS-CoV-2 infection
- a high-risk contact with a confirmed SARS-CoV-2 case

- social contacts (number of contacts during the last 7 days outside the school environment and outside the household, including travelling abroad)

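### Symptom status is not tied to the positive sample, so index children can be misclassified for endpoint 2, and for endpoint 1 as section 3.4 words it

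*Combined protocol and SAP*

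**What the plan says.** Section 4.4.3.1 gives two definitions. An asymptomatic case is "a participant who has a positive salivary test for SARS-CoV-2 during the study period and who did not declare any symptoms compatible with COVID-19". A symptomatic case is "a participant who has a positive salivary test with symptoms compatible with COVID-19 during the study period".

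Section 5.2 collects the symptom information by a follow-up questionnaire completed "once a week for six consecutive weeks", asking about "any compatible symptom with a SARS-CoV-2 infection". Its description states no link to the date of a positive sample.

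Status then decides who can be an index case. Endpoint 2 in section 3.4 is "Time varying number and proportion of adult school-attenders infected with SARS-CoV-2 secondary to an asymptomatic infected child", and the synopsis restricts it in the same way. For endpoint 1 the two places differ. Section 3.4 has "Time varying number and proportion of children infected with SARS-CoV-2 secondary to an asymptomatic infected classmate", while the synopsis has "Time varying number and proportion of children infected with SARS-CoV-2 secondary to an infected classmate".

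Section 4.4.3.2 also depends on status. Contacts are counted over the 48 hours before symptom onset or, for asymptomatic participants, over the 48 hours before the positive test.

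**The concern.** Followed as written, the definitions can go wrong in two directions.

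- A child who is positive in week 1 without symptoms and reports a cold in week 6 becomes symptomatic, and so drops out as an index case wherever the index must be asymptomatic.
- A positive child who had symptoms but returned no questionnaire has declared none, and so is asymptomatic by default.

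Classification therefore depends partly on how many questionnaires a family returns. This matters because transmission from asymptomatic children is a stated objective in the synopsis, and section 2.0 presents it as the gap in existing data. The label can also move the contact window of section 4.4.3.2. For the week-1 positive with a week-6 cold, a window anchored on symptom onset would lie about five weeks after the infection that was detected, and the wrong contacts could be linked to it.

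**Working it through.** **The plan's own figures.** The plan gives no rate of unrelated symptoms, no expected asymptomatic share and no misclassification figure, so there is nothing to reproduce on this point. The nearest number is the 120-240 expected cases in section 7.1. With 2400 children, 0.5-1% gives 2400 × 0.005 = 12 to 2400 × 0.01 = 24 per round, or 72-144 over six rounds, so it does not reproduce over six rounds. That is a separate matter. The results below are shares of truly asymptomatic cases and do not use it.

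**Is there a window elsewhere?**
- Section 4.4.3.1: the symptom clause of the asymptomatic definition has no time limit. In the symptomatic definition the study period is the only time reference.
- Section 4.4.3.2: the 48-hour rule defines contacts, not case status.
- Section 5.0: the interviews about absences carry no rule for reclassifying a case.
- Section 5.2: symptoms are reported weekly for six weeks. The section lists no compatible symptoms and gives no rule for symptoms with another cause.

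No other window is stated.

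**Inputs for the illustration.**
- k = 6 questionnaires (section 5.2). The topics listed for the inclusion questionnaire in section 5.1 contain no symptom item, so I do not count a seventh.
- s = weekly probability of an unrelated compatible symptom. This is assumed; I show 2%, 5% and 10%.
- Weeks are taken as independent and every questionnaire as returned.

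**Formula.** Share of truly asymptomatic cases relabelled = 1 − (1 − s)^k.

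| s (assumed) | six questionnaires | three questionnaires | difference (points) |
|---|---|---|---|
| 2% | 1 − 0.98^6 = 11.4% | 1 − 0.98^3 = 5.9% | 5.5 |
| 5% | 1 − 0.95^6 = 26.5% | 1 − 0.95^3 = 14.3% | 12.2 |
| 10% | 1 − 0.90^6 = 46.9% | 1 − 0.90^3 = 27.1% | 19.8 |

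Per 100 truly asymptomatic cases, the whole-period reading keeps 88.6, 73.5 or 53.1, and a three-questionnaire window keeps 94.1, 85.7 or 72.9.

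**Dependence on response.** Under the whole-period reading the exponent is the number of questionnaires returned. At s = 5%, a child returning six has a 26.5% chance of being relabelled, one returning three has 14.3%, and one returning none has 0%. A truly symptomatic child returning none is counted as asymptomatic. The two errors act in opposite directions on the size of the asymptomatic index set.

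**The case against.** The strongest reply is that the text is ambiguous rather than wrong. In the asymptomatic definition the study period qualifies the test, not the symptoms. A positive test with symptoms can be read as symptoms accompanying that positive result, and a sensible analyst would apply some window. This stands in part: the week-6 cold example needs the literal reading. But any other reading requires a window that is not written, and that could be chosen after the data are seen.

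A reader might infer more than the documents support:

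- **That endpoints 1 and 2 are both compromised throughout.** Only endpoint 2 is restricted to asymptomatic index children in both endpoint lists. The outcomes in section 3.2 carry no such restriction.
- **That a planned contrast between symptomatic and asymptomatic index cases is blurred.** Section 7.1 compares gender, age and kinds of school, and plans no such contrast.
- **That the attack rate per index case is necessarily biased.** If colds are unrelated to transmission, dropping those index cases lowers endpoint counts and precision but does not in itself bias the rate among those kept.
- **That the asymptomatic set must shrink overall.** Relabelling shrinks it; default labelling of non-responders enlarges it. The net effect is not determined.

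It is also fair to say that a long symptom-free requirement helps keep pre-symptomatic children out of the asymptomatic group, and that the absence interviews may supply some symptom information. Neither provides a classification rule. Finally, this is a descriptive pilot, which limits the consequences without removing the need for a clear definition.

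**Conclusion.** The point holds. Symptom status, which selects index cases for endpoint 2 and for endpoint 1 as section 3.4 words it, is not tied to the positive sample. Taken literally, the definitions misclassify in both directions, partly according to questionnaire return, and can shift the contact window.

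That conclusion rests on the text alone. The size does not: 11%, 26% or 47% relabelled over six questionnaires, against 6%, 14% or 27% over three, holds only under the assumed weekly rates, independent weeks and full response. Symptoms that persist or cluster in the same child, or missed questionnaires, would lower these figures. A shorter window reduces the problem but does not remove it. It is worth correcting because the correction is cheap, not because the loss is known to be large.

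**What to change.** In section 4.4.3.1, define status relative to the first positive sample, using a pre-specified window, for example the questionnaires for the week before, the week of and the week after that sample. Use mutually exclusive groups:

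- **Symptomatic:** a compatible symptom at or before the positive sample, within the window.
- **Pre-symptomatic:** first symptom only after the sample, within the window.
- **Asymptomatic:** the questionnaires in the window returned, with no symptom.
- **Unclassified:** no symptom reported and a required questionnaire missing.

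Say how a symptom in the week of the sample is placed before or after it, by onset date if the questionnaire records one and otherwise by a stated convention. For inclusion-day positives use only the weeks available. Final-round positives need one further symptom report; the absence interviews, which already run until two weeks after the end of the study, could be extended to cover it.

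Reconcile the synopsis and section 3.4 on whether endpoint 1 requires an asymptomatic index child. Add a sensitivity analysis using all infected index children whatever their symptom status.

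Cost: one paragraph in 4.4.3.1, one wording change to endpoint 1, one sensitivity analysis and one additional symptom report for final-round positives. The remaining data are already planned weekly. The downside is a group, probably small, that stays unclassified.

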4.4.3.2 High versus low risk contact

Definitions of high or low risk contact in the present study are the same as the national definition edited by Sciensano (version 1 october 2020)

https://covid-19.sciensano.be/sites/default/files/Covid19/COVID-19_procedure_contact_FR.pdf

- High risk contact is defined as
 - a person who had face to face contact for at least 15 minutes within a distance of 1.5 meter, without wearing mask or
 - a person with a physical contact
 - a contact with secretions or body fluid
 - who has travelled with a COVID-19 patient for at least 15 minutes, in any vehicle, seated two seats apart

with the index case within the 48 hours before the onset of symptoms, or in the last, 48 hours before the positive test, in case of asymptomatic participants

- Low risk contact is
 - a person who had face to face contact for at least 15 minutes within a distance of 1.5 meter, and wearing the mask correctly
 - a person who had face to face contact for less than 15 minutes within a distance of 1.5 meter (face to face) or
 - a person in the same room for at least 15 minutes with a distance more than 1.5 meter

with the index case within the 48 hours before the onset of symptoms, or in the last, 48 hours before the positive test, in case of asymptomatic participants

School attenders in primary school are wearing a mask when the social distancing cannot be maintained.

5.0 Conduct of the study

Parents and children attending selected schools will be informed of the exact nature of the study with a written version of participant information transmitted by the school director. Parents and children will be invited to participate in a virtual zoom (professional version with secured password) meeting. During this meeting the study objectives, procedures and implications will be explained to the teachers, parents and children. Where/When feasible a

video adapted to each school will be posted on the virtual school platform to be able to reach the maximum of parents and children. Written informed consent will then be obtained from the participants and/or their legal guardian.

Once a week and for six consecutive weeks, all participants of the school will be invited to provide a self-sampled salivary specimen, in the schools and under supervision of medical students on contract.

Currently, procedures only identify symptomatic cases. Interferences with current guidelines will impact results of this study as symptomatic cases and asymptomatic participants with a high-risk contact would be excluded from schools. Indeed, systematic saliva samples will not

Results of the salivary PCR SARS-CoV2 will not be communicated to participants during the study period. Salivary samples of the study will not be analysed routinely but will be treated in batch according to the laboratory capacity of the national platform BIS. The estimated time between sample collection and the availability of the result will be more than a week. Clinical relevance and societal repercussions of the communication to a participant of a positive result so long afterward will be irrelevant. Indeed, it is currently recognized by most experts that contagiousness lasts 7 days after the onset of symptoms. In a study from Taiwan of 100 COVID-19 cases and 2761 close-contacts, secondary attack rates was significantly higher among contacts whose exposure to the index case started within 5 days of symptom onset compared with those exposed later (no secondary cases among the 852 contacts exposed to index case after day 6 of symptom onset) (18).

It is important to stress that participation to the present study does not exclude participants to follow the national recommendations as detailed in Sciensano procedures, namely a test performing in case of compatible symptoms of SARS-CoV-2 infection or a quarantine in case of a high-risk contact. Investigators will also insist to students and school attenders on the importance of non-pharmaceutical interventions, including physical distancing and mask to prevent SARS-CoV-2 transmission as recommended by Sciensano.

Protocols (ONE as in the Ministry of Education's circular) will be applied as per the standard procedures. The decision to close a classroom will be taken by the PSE and if needed after concertation with the hygiene control inspector of COCOM or AVIQ.

To investigate a possible link between the absence from school of a participant and SARS-CoV-2 infection, the PSE team member will interview this participant later. This interview will continue until 2 weeks after the end of the study to complete data collection.

Any salivary PCR SARS-CoV2 test that comes back positive (with a maximum Ct of 30) will be analysed by a Whole Genome Sequencing (WGS) of the SARS-CoV2 virus (exploratory outcome). Phylogenetic analysis of the virus is expected to determine transmission linkages between cases and to map transmission patterns inside households and at school.

5.1 Inclusion day

All participants, children and adults school attenders, will be tested at the inclusion day with

- a salivary SARS-CoV2 PCR test collected in the school, under investigators supervision
- a rapid serological test by finger prick (AVIOQ[®]) to determine the seroprevalence of SARS-CoV-2
- All participants (children and adult school attenders) will be invited to complete an electronic questionnaire when possible and a paperback questionnaire otherwise.

The questionnaire will address the following information (see attached file) partially inspired of the questionnaire used in the prevalence study *“Prevalence and incidence of antibodies against SARS-COV-2 in children measured for one year in Belgium: a sero-epidemiological prospective cohort study”* (study coordinator: [name], Sciensano).

- Socio-demographic data: gender, birth date, home postal code, a contact email address, a contact mobile number, country of birth of child and parents
- Housing information: number of people in the household, number of siblings, number of sleeping rooms, distance between school and home
- Exposition information: pre- and after-school daycare attending, extracurricular activities, parent's profession, transportation means between home and school

The salivary SARS-CoV2 sample will be performed at school by the participant him or herself under the supervision of the subinvestigators (80 medical students on contract) for minor

participants. An explanatory film on the method of self-performing the saliva sample will be provided to participants. The children and the teachers will use a garling method to produce saliva. The full procedure is explained in the explanatory film. The participant will wear an adapted mask while gargling. A full explanation of the used gargling sampling technic is also well detailed in the attached paper (19)

The procedure will be performed in a well-ventilated space one participant at a time. The medical student who will collect the sample will wear adapted personal protective equipment (PPE) in order to reduce the risk of transmission to as good as 0. The PPE will include FFP2 mask, gloves, glasses and a protective gown.

After collection, salivary samples will be transported to one of the three participating laboratories (UCLouvain - ULiège - ULB) by the medical student.

Teachers of each class will be invited to complete a questionnaire once with the following questions

- Number of children in the classroom
- Size of the classroom
- Ventilation system and heating system of the classroom (CO2 sensor if any)
- Sanitary protocols of the school: eg hand washing recommendations
- Play-time space: indoor or outdoor
- Lunch space: in the classroom, school cafeteria, etc
- Organisation of pre- and after-school daycare attending: separation according to levels or mix of all classes. Number of children attending.

5.2 Follow-up visit

All participants, children attending selected schools and adults school attenders, will be asked to provide a weekly salivary specimen for six consecutive weeks.

All participants, children attending selected schools and adult school attenders, will have to complete a follow-up questionnaire, once a week for six consecutive weeks (See attached file) providing information about

- any compatible symptom with a SARS-CoV-2 infection
- a high-risk contact with a confirmed SARS-CoV-2 case

- social contacts (number of contacts during the last 7 days outside the school environment and outside the household, including travelling abroad)

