7.0 Statistical analyses plan

7.1 Sample size and statistical analysis

As a pilot study, no formal sample size determination was performed. The expected number of children is 2400 (4 times 200 plus 4 times 400), the expected number of adult school attenders is 200, and the expected number of classes is 72. With an incidence around 0.5-1%, the expected number of cases is 120-240. Initial incidence and then secondary attack rates (as transmission estimator) will be calculated and compared between gender, across age, and between the three kinds of schools using Poisson or Binomial negative regression if overdispersion. Characteristics of classes will be compared between schools using ANOVA with F-tests for continuous variable and chi-square or Fisher exact tests for discrete variables. Any significant difference will be considered for correlation with incidence rates (per classes) and attack rates within the Poisson or Binomial negative regression. A cluster effect (Rho = 1.09 or ICC=0.09) will be assessed for weighting data analysis. Estimates will be presented with their 95% Confidence interval. Differences will be presented as absolute and relative differences.

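### The secondary attack rate has no follow-up requirement for index cases found in the last saliva rounds, so by default the in-school rate is biased low

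*Combined protocol and SAP*

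**What the plan says.** **Sampling.** Section 5.1 provides for "a salivary SARS-CoV2 PCR test collected in the school, under investigators supervision" on inclusion day. Section 5.0 then sets the weekly schedule: "Once a week and for six consecutive weeks, all participants of the school will be invited to provide a self-sampled salivary specimen". Section 5.2 repeats it: all participants "will be asked to provide a weekly salivary specimen for six consecutive weeks". Depending on whether inclusion day counts as week one, there are six or seven rounds. No later round is planned. Section 5.0 also says that samples are analysed in batches with results after more than a week, so a late positive would not prompt extra sampling.

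**Case definition.** Section 4.4.3.1 defines a positive case as "a participant who has a positive PCR salivary test for SARS-CoV-2 detected by systematic weekly screening".

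**After the last round.** Section 5.0 provides an interview by the school health team, with the purpose "To investigate a possible link between the absence from school of a participant and SARS-CoV-2 infection". On its duration: "This interview will continue until 2 weeks after the end of the study to complete data collection". No specimen is attached to it.

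**Analysis.** Section 7.1 states: "Initial incidence and then secondary attack rates (as transmission estimator) will be calculated and compared between gender, across age", and also between kinds of schools. It gives no risk window, no denominator and no rule for index cases found near the end. Section 3.4 describes its first endpoint as "Time varying number and proportion of children infected with SARS-CoV-2 secondary to an asymptomatic infected classmate", without saying whether a weekly value belongs to the week of the index case or of the secondary case.

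**The concern.** Most secondary cases will turn positive at a round after their index case. An index case first positive at the last round has no later round, and one found at the round before has a single later round. Their contacts can be infected without that ever becoming a case under section 4.4.3.1. The absentee interview does not repair this: it takes no sample, and it cannot find an asymptomatic secondary case in a child who is still attending, which is the kind of transmission the study was set up to measure.

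If such index cases stay in the denominator, the in-school attack rate is too low. The Synopsis hypothesises a school rate at least five times lower than the household level, so the error favours the hypothesis. The share of incompletely followed index cases also depends on each school's epidemic curve, so schools with the same true attack rate could appear to differ.

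**Working it through.** **The plan's own figures.** The documents give no expected attack rate, lag distribution or follow-up window, so there is no truncation figure to reproduce. The only derived figure in section 7.1 is 120-240 expected cases at an incidence of 0.5-1%. It does not follow from 2400 children: 2400 × 0.005 to 0.01 gives 12-24 for one period, 72-144 over six weeks and 84-168 over seven. Nothing below uses it.

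**Inputs.** The number of rounds R is 6 or 7 (sections 5.0, 5.1, 5.2). My assumptions, since the documents give none: a share *a* of secondary cases first tests positive one round after the index case and 1 − *a* two rounds after; incidence is flat unless stated; all index cases stay in the denominator.

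**Step 1, flat incidence.** Index cases of the first R − 2 rounds are fully observed, those of the next-to-last round contribute *a*, and those of the last contribute 0. Hence observed/true = (R − 2 + *a*)/R.

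| Rounds | *a* = 1 | *a* = 0.5 |
|---|---|---|
| 7 | 6/7 = 0.857, loss 14% | 5.5/7 = 0.786, loss 21% |
| 6 | 5/6 = 0.833, loss 17% | 4.5/6 = 0.750, loss 25% |

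**Step 2, changing incidence (R = 7, *a* = 0.5).** Loss = share in last round + 0.5 × share in next-to-last round.
- Rising 20% per week (weights 1.2^k, k = 0 to 6): 23.1% + 0.5 × 19.3% = 32.8%.
- Falling 20% per week (weights 0.8^k): 6.6% + 0.5 × 8.3% = 10.8%.

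Two schools with the same true attack rate, one on each curve, would show 0.672 and 0.892 of it. Their ratio is 0.672/0.892 = 0.75, an apparent 25% difference with no real one. Over a wider set (six or seven rounds, weekly factors 0.7 to 1.3, several lag patterns), the loss ran from 4% to 40%.

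**Step 3, same-round positives.** Suppose 20% of secondary cases appear in the index case's own round, 60% one round later and 20% two rounds later. With R = 7 and flat incidence the loss is (0.8 + 0.2)/7 = 14%; with R = 6 it is 1/6 = 17%. The pooled bias remains, but the last index week shows 0.20 of its true value rather than zero.

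**Step 4, the hypothesised ratio.** If only the school rate were truncated, a true ratio of 5 would appear as 5/0.857 = 5.8 to 5/0.750 = 6.7 under flat incidence.

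**Step 5, restricting the denominator.** Leaving out index cases of the last two rounds gives observed/true = 1.00 in every scenario; this is by construction, as no assumed lag exceeds two rounds. Leaving out only the last round gives, for flat incidence and *a* = 0.5, 5.5/6 = 0.917 (R = 7) or 4.5/5 = 0.900 (R = 6), and 0.84-1.00 over the wider set.

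**The case against.** The strongest reply is that the plan is silent rather than wrong. It defines a positive case but not an index case, and nowhere says that contacts of last-round index cases enter the denominator. That is fair. The bias follows from the default reading, that nothing is excluded, and not from stated text.

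A reader might infer that the last weekly value is forced to zero. The documents do not support this. It needs weekly values dated by the index case and same-round positives never counted as secondary, and the plan fixes neither. Section 3.4 describes the infected person, which reads at least as naturally as dating by the secondary case. The last round is then not affected; it is the first round that lacks an earlier sample to link to. With weekly sampling, two linked cases can also turn positive together, and the weekly questionnaires and exploratory sequencing might help to order them.

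A reader might also infer that there is no follow-up at all after the last round. The absentee interview exists, although it cannot yield a case under the plan's definition.

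The size rests on assumed lags and curves. Inclusion-day PCR also picks up prevalent infections. If that round held twice a normal week's positives, the last round would hold 1/8 = 12.5% of index cases, and the loss would be 12.5% to 12.5% + 6.25% = 19%, slightly below the seven-round range. This moves the figure but not its direction.

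**Conclusion.** The concern holds in conditional form. Sampling ends with the last round, only screening positives count as cases, and no follow-up requirement applies to index cases. With late index cases in the denominator, the in-school secondary attack rate is understated by about 14-21% (seven rounds) or 17-25% (six rounds), given flat incidence and lags of one to two rounds. The loss is larger when incidence rises and smaller when it falls, so school comparisons are exposed too.

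The time-varying endpoints are affected only if dated by index case: the last week would then be near zero and the one before it too low, which could be misread as falling transmission. The inflated five-fold ratio in the working is also conditional, since the plan does not say how the household level is estimated or whether it is truncated in the same way.

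Pilot status explains the absence of a formal sample size. It does not justify an avoidable bias in the transmission estimator.

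**What to change.** In section 7.1, state that:
- all rounds count for detecting infections, but only index cases first positive at least two rounds (14 days) before the school's last sampling round enter the primary secondary attack rate;
- a one-round (7-day) rule and an analysis of all index cases are sensitivity analyses;
- the time-varying endpoints are dated either by index case or by secondary case. If by index case, flag the last index week as not estimable and the week before as incompletely followed. If by secondary case, keep all weeks, since blanking the last ones would discard valid data.

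This needs analysis-plan wording only, with no new samples or visits. The cost is precision. Under flat incidence 2/7 = 29% or 2/6 = 33% of index cases leave the primary denominator. With interval width proportional to 1/√(number of index cases), intervals widen by 1/√(5/7) = 1.18 to 1/√(4/6) = 1.22, that is 18-22%. If incidence rose 20% per week over seven rounds, 23.1% + 19.3% = 42.4% would leave, and the widening would be 1/√0.576 = 1.32.
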